#### 3.3. MODEL DEVELOPMENT

The following procedures will be applied for the development of the two prognostic models. Information from all subjects in the Massachusetts General Hospital database will be used to develop the two predictive models proposed in this analysis plan. Both models will predict the same outcome (Atrial Fibrillation) after cardiac surgery but will differ in the predictors they use to predict the outcome.

#### 3.3.1. Study setting and data collection

We will use the Massachusetts General Hospital (MGH) database to develop the PARADISE prediction models. The MGH dataset has two data sources:

- 1. the Research Patient Data Registry (RPDR): medical record data extracted from electronic hospital systems
- 2. the Society of Thoracic Surgeons (STS) Adult Cardiac Surgery Database: data gathered by trained extractors

Both data sources for the Mass General Hospital dataset will be used to develop our models and we will use retrospective pre-, intra-, and post-operative data for over 10,000 cardiac surgeries performed and recorded at this single US centre between 2003 and 2020.

It is important to note that some tables from this dataset were affected by a change in its electronic medical record system, which changed from Longitudinal Medical Record (LMR) to EPIC in April 2016.

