#### 3.3.2. SAMPLE SIZE CALCULATION

As the two models to be developed are predicting the same outcome (new onset AF in the 7 days after surgery), the same sample size is applicable to both models.

Data on approximately 12,000 surgeries are available from Massachusetts General Hospital between 2003 – 2020 with approximately 20% of patients having new onset AF in the 7 days after surgery.

We used formal sample size formulae for binary outcome measurement provided by Riley et al [28] and the associated 'pmsampsize'[29] sample size calculator in R statistical software programme to calculate the maximum number of candidate predictor parameters we can include during model development. Based on the prevalence and assuming an anticipated R squared between 5% and 15% of the max Cox-Snell R2 (i.e. Cox-Snell R2 between 0.0316 and 0.0948) we can examine up to 42 - 132 predictor parameters for inclusion in the model [28].

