#### 3.3.4. DURING MODELLING

In the Massachusetts General Hospital dataset, we anticipate that around 18% of patients will experience AFACS which was used to inform the sample size calculation. We will model the binary outcome using logistic regression. Though the risk of overfitting is low, given the high number of candidate predictors, we will also use shrinkage methods and specifically the Least Angle Selection and Shrinkage Operator (LASSO) to penalise and identify which predictors will be included in the final models [30].

Continuous variables will be kept as continuous in the model to avoid a loss of predictive information. Non-linear relationships with AFACS will be investigated using fractional polynomials or restricted cubic splines.

Since the development cohort spans an extended period, there is a chance that the calibration of the model will vary according to time. Therefore, we may consider re-calibrating the final model using the most recent subset of data [31].

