#### 3.4. GENERAL ISSUES FOR STATISTICAL ANALYSIS

#### 3.4.1. METHOD FOR HANDLING MISSING DATA

To avoid excluding patients when developing and validating our models, we will use multiple imputation to impute missing values, under a missing at random assumption.

Identifying the true underlying missing data mechanism from the available is rarely possible. Assumptions need to be made on the plausible mechanism, and approaches needed to be used. Under a missing completely at random mechanism. (MCAR), the missingness mechanism does not depend on unobserved (unseen) data. Conducting a complete case analysis will produce unbiased estimates (but with a loss precision if full data are observed). Under the missing at random (MAR) assumption, the missingness after conditioning on the observed data does not depend on the unobserved (unseen) data. Under this approach, we can apply approaches such as multiple imputation, by fitting a joint model to the observed data and impute the missing data, taking account of the uncertainty in the estimated parameters of this joint model.

We feel this, MAR, approach makes a less strong and more realistic assumption than the MCAR approach. The MAR imputation model will include all variables considered for the multivariable model building, the outcome and any auxiliary variables that will help explain the missingness. The assumption of a missing not at random (MNAR) approach whilst not implausible is considerably more complex to investigate – there is a dearth of research investigating MNAR in the context of prediction model research. We will nevertheless explore whether the MAR assumption holds by comparing the imputed values (after accounting for the observed values) and the missing values to identify if there are any systematic differences to suggest a MNAR assumption.

Therefore, to conform to current guidelines[34], multiple imputation for all subjects with at least one missing value (using the 'mice' function in R, for example) will be used.

Data from LHCH and BHC provide a large "real-world" prospective validation but is likely to contain more missingness [35].

Using sensitivity analyses we may investigate the impact of informative missingness in our model development, i.e. departures from the missing at random assumption.

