#### 3.5. INTERNAL VALIDATION

After developing a prognostic model, it is important to evaluate its performance. Internal validation can be performed using methods applied to the same data from which the model was developed. Internal validation of the final model will also be assessed by the bootstrap resampling technique using at least 200 iterations whereby each modelling step is repeated in each bootstrap sample, to adjust for over-optimism in the estimation of model performance. ML models will also be additionally validated via k-fold cross-validation. The internal validation will quantify and be used to adjust the performance measures (e.g., discrimination, calibration) for any optimism.

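### The SAP names a 2016 record-system change and possible calendar drift, but no check within the development data is ordered by time

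*SAP*

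**What the plan says.** SAP 3.3.1 describes the development data as surgeries "performed and recorded at this single US centre between 2003 and 2020". It warns that "some tables from this dataset were affected by a change in its electronic medical record system", and that this system "changed from Longitudinal Medical Record (LMR) to EPIC in April 2016". It does not say which tables. SAP 3.3 pools the eras: "Information from all subjects in the Massachusetts General Hospital database will be used to develop the two predictive models". SAP 3.3.4 accepts that calibration may vary over so long a period. Its response is that "we may consider re-calibrating the final model using the most recent subset of data", with no trigger, window or method.

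SAP 3.5 plans a bootstrap of at least 200 iterations in which "each modelling step is repeated in each bootstrap sample", plus k-fold cross-validation for the machine-learning models. Neither is defined by calendar time. The internal-external cross-validation at the end of SAP 3.8 runs across hospitals, and the development set has one hospital.

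Three other provisions bear on the point:
- SAP 3.2 counts AF as present if it is found in a cardiac report or by a trained STS abstractor.
- The imputation model in SAP 3.4.1 "will include all variables considered for the multivariable model building, the outcome and any auxiliary variables" that help explain missingness.
- SAP 3.8 commits to external validation in Brigham (2001-2016), Tight K and prospective NHS data, and to investigating recalibration for the UK population. The protocol synopsis places the primary outcome in external data and dates the prospective sub-study October 2021 to July 2023.

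**The concern.** The plan identifies a dated threat to its development data and then commits to no analysis there that could detect it. A bootstrap of the pooled years reproduces the mixture of eras in every resample. It measures overfitting to that mixture, not whether the model fits the later part of it. K-fold with folds not set by date has the same blind spot.

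One of the two data sources is extracted from electronic hospital systems, and AF is read partly from cardiac reports. Predictor recording, missingness and AF capture could therefore each have changed in April 2016. The scores are meant for patients treated now, and SAP 3.7 evaluates net benefit at a 25% risk threshold, so an error in the level of predicted risk moves patients across that line. If drift first shows in the UK data, it arrives mixed with differences in country, case-mix and AF ascertainment.

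**Working it through.** **Inputs.** SAP 3.3.2: "Data on approximately 12,000 surgeries are available from Massachusetts General Hospital" (3.3.1 says over 10,000), with AF in about 20% (3.3.4 says about 18%). Period 2003-2020, switch in April 2016 (3.3.1). Precision targets from SAP 3.8.2: 95% CI widths of 0.2 for O/E, 0.2 for slope and 0.1 for C. Assumed: even accrual, and the sizes of shift below.

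**1. The plan's own precision figures.**
- O/E: n = (1-p)/(p x SE^2) = 0.8/(0.2 x 0.051^2) = 1,538, as stated.
- C, using Var(C) = C(1-C)[1 + (n/2-1)(1-C)/(2-C) + (n/2-1)C/(1+C)] / [n^2 p(1-p)] and SE 0.0255: n = 619 at C = 0.72, as stated.
- Slope, from the logistic information matrix with a normal linear predictor: 4,414 at C = 0.72 and 4,245 at C = 0.725, against 4,248 stated. The difference is within the rounding of C.

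**2. Surgeries after the switch.** January 2003 to March 2016 is 13.25 of 18 years, or 73.6%; 26.4% follow.
- N = 12,000: 12,000 x 4.75/18 = 3,167 (633 events at 20%, 570 at 18%).
- N = 10,000: 2,639.
- If data stop at the start of 2020: 3.75/18 gives 2,500 and 2,083. These are low-side figures, because a 17-year span gives 12,000 x 3.75/17 = 2,647 and 10,000 x 3.75/17 = 2,206.

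The working range is about 2,080 to 3,170.

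**3. What a shift in recorded AF would do.** With case-mix unchanged, a model without an era term predicts the pooled incidence in both eras.
- 19% to 21%: pooled 0.736 x 0.19 + 0.264 x 0.21 = 0.195. Later-era O/E = 0.21/0.195 = 1.08; intercept error logit(0.21) - logit(0.195) = 0.09.
- 18% to 25%: pooled 0.736 x 0.18 + 0.264 x 0.25 = 0.198. O/E = 0.25/0.198 = 1.26; intercept error 0.30. A predicted 25% would then correspond to about 31%, since logit(0.25) + 0.30 = -0.80.

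**4. Can the bootstrap see it?** A simulation used 12,000 patients, 26.4% of them in the later era, 40 predictors (12 informative), unpenalised logistic regression and 200 bootstraps, with one run per scenario. Cells show O/E and slope.

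| Assumed change at the switch | Bootstrap-corrected | All-years model, new later-era patients | Early-era model tested on later era |
|---|---|---|---|
| None | 1.00, 0.96 | 0.98, 1.00 | 0.96, 0.84 |
| AF 21.5% to 16% | 1.00, 0.97 | 0.80, 0.94 | 0.75, 0.89 |
| AF 18% to 25.6% | 1.00, 0.97 | 1.28, 1.02 | 1.39, 1.04 |
| 4 informative predictors become noise | 1.00, 0.96 | 0.96, 0.74 | 1.02, 0.57 |
| AF 21.5% to 16% and 4 become noise | 1.00, 0.95 | 0.81, 0.79 | 0.74, 0.63 |

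The bootstrap column is almost constant while later-era performance moves. The hold-out shows each problem, but it exaggerates the O/E error of the all-years model (1.39 against 1.28), because its model saw no later-era patients. Its slope is noisy: 0.84 with no drift at all.

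**5. Precision of a later-era test (2,080 to 3,170 surgeries, 20% AF).**
- O/E width 3.92 x sqrt(0.8/(0.2n)) = 0.17 to 0.14; target 0.2, met.
- C width 0.054 to 0.044; target 0.1, met.
- Slope width by scaling, 0.2 x sqrt(4,248/n) = 0.29 to 0.23; target 0.2, missed.

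**The case against.** A reader might infer that a miscalibrated model could pass the study's decisive test. The documents do not support that. The primary outcome is performance in external data. The NHS cohort is recent and large: about 6,000 patients a year, against the SAP's own minimum of 4,248. The SAP also says it will investigate UK recalibration, so only temporal recalibration is left optional. These points stand and limit the consequence for UK use. They do not supply a test of drift within the development hospital. Nor do they separate drift from US-UK differences.

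The US validation set could give a hint. In the 18% to 25% case, patients at 18% would show O/E of about 0.18/0.198 = 0.91. But Brigham is a different hospital with a CABG database ending in 2016, so the hint would be confounded, and post-switch US patients are never examined as a group.

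A reader might also infer that AF capture did change in 2016. The SAP says only that some tables were affected, and the abstractor route to the outcome could dampen any change in the reports. The shifts above are illustrations.

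Nor does the imputation plan shut out time: its auxiliary-variable clause already admits surgery year or record era. Adding era would not repair a field recorded in only one system, because era is then constant among the observed values.

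Finally, an automatic recalibration rule based on confidence intervals would be unsound. In the no-drift run the hold-out slope of 0.84, with a half-width of 0.12 to 0.145, would have triggered it. The trigger would come from a different model than the one recalibrated, and recalibrating to a recording artefact would build the artefact in.

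**Conclusion.** The gap is real and moderate. The SAP flags two time-related threats, but no planned analysis within the development data is ordered by time, and the one temporal remedy is undefined. Drift there could go undetected until the UK validation, where its cause would be hard to identify. Its size cannot be known from the documents: later-era O/E of about 1.08 or 1.26 follows from assumed shifts of 19% to 21% or 18% to 25%, with even accrual and stable case-mix. The simulation rests on single unpenalised runs rather than the planned LASSO; its O/E contrast is firmer than its slopes. This does not invalidate the study or its external validation. It is an improvement in prespecification that the data already held can support.

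**What to change.** In SAP 3.5, beside the bootstrap results:
1. Add a time-ordered validation: repeat the modelling steps on 2003 to March 2016, then report O/E or intercept, C and slope on April 2016 to 2020.
2. Report the final all-years model's calibration by era or calendar year.
3. Compare AF capture by source (cardiac report versus STS abstractor) and predictor missingness before and after the switch, and list any field recorded in only one system.

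In SAP 3.3.4, define the recent subset and say how the recalibration decision will be made. It should rest mainly on the final model's O/E or intercept in the later era, with slope as supporting evidence because of its wider interval. It should be taken only after item 3 has been used to check that the shift is not a recording artefact. No automatic trigger is needed.

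The cost is SAP wording and one extra fit per model on data already held. The final model still uses all years. Reported internal performance may look slightly less favourable.

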#### 3.3.2. SAMPLE SIZE CALCULATION

As the two models to be developed are predicting the same outcome (new onset AF in the 7 days after surgery), the same sample size is applicable to both models.

Data on approximately 12,000 surgeries are available from Massachusetts General Hospital between 2003 – 2020 with approximately 20% of patients having new onset AF in the 7 days after surgery.

We used formal sample size formulae for binary outcome measurement provided by Riley et al [28] and the associated 'pmsampsize'[29] sample size calculator in R statistical software programme to calculate the maximum number of candidate predictor parameters we can include during model development. Based on the prevalence and assuming an anticipated R squared between 5% and 15% of the max Cox-Snell R2 (i.e. Cox-Snell R2 between 0.0316 and 0.0948) we can examine up to 42 - 132 predictor parameters for inclusion in the model [28].

#### 3.3.4. DURING MODELLING

In the Massachusetts General Hospital dataset, we anticipate that around 18% of patients will experience AFACS which was used to inform the sample size calculation. We will model the binary outcome using logistic regression. Though the risk of overfitting is low, given the high number of candidate predictors, we will also use shrinkage methods and specifically the Least Angle Selection and Shrinkage Operator (LASSO) to penalise and identify which predictors will be included in the final models [30].

Continuous variables will be kept as continuous in the model to avoid a loss of predictive information. Non-linear relationships with AFACS will be investigated using fractional polynomials or restricted cubic splines.

Since the development cohort spans an extended period, there is a chance that the calibration of the model will vary according to time. Therefore, we may consider re-calibrating the final model using the most recent subset of data [31].

#### 3.3.5. ASSUMPTION CHECKS

The normality of residuals will be checked using graphical methods. Influence of individual data points will be assessed by plotting leverage residuals against fitted data.

#### 3.3.6. MACHINE LEARNING APPROACHES

In parallel to develop statistical prediction models, we will investigate machine learning (ML) approaches to developing a prediction model, including methods such as random forests, deep neural networks, and Bayesian Gaussian processes. Such models allow consideration of interactions between available variables providing "latent variables" (complex, non-linear transformations of the original input variables) that may improve prediction performance over the non-transformed input variables. We will prioritise principled, probabilistic methods that permit the incorporation of prior clinical knowledge, such that results are "interpretable", avoiding the "black box" nature of much ML-oriented research in this area [32, 33].

We will exploit the ability of the complementary modern ML fields of (i) Bayesian non-parametric modelling (which provides a principled means of coping with artefact and measurement noise in the clinical data) and (ii) deep learning, which permits the fusion of large quantities of (potentially time-varying) clinical variables. These models include components ("attention mechanisms") that allow the resulting risk estimations to be interpretable for clinicians.

Importantly, these models permit the model to quantify its uncertainty in its score prediction – where conventional medical statistical methods always output a score, ML models provide the opportunity to quantity probabilistically the certainty with which a score is produced; this offers advantages in applications in which classes are substantially overlapped, as often occurs in complex, real-world clinical problems, where there is imperfect class separation. Accuracy of such models can often be substantially improved by permitting a model not to make a classification if the score is highly uncertain; such approaches are used in many application areas of critical systems to improve acceptability with users.

Additionally, we will investigate the joint construction of phenotypical clustering models (which identify reproducible phenotypes in the physiological data) with predictive models specific to each phenotypical group – this novel approach constructs an ensemble of predictive models that are phenotype-specific, thereby improving predictive accuracy with respect to a single "one-size-fits-all" generic algorithm applied to the entire population.

#### 3.4. GENERAL ISSUES FOR STATISTICAL ANALYSIS

#### 3.4.1. METHOD FOR HANDLING MISSING DATA

To avoid excluding patients when developing and validating our models, we will use multiple imputation to impute missing values, under a missing at random assumption.

Identifying the true underlying missing data mechanism from the available is rarely possible. Assumptions need to be made on the plausible mechanism, and approaches needed to be used. Under a missing completely at random mechanism. (MCAR), the missingness mechanism does not depend on unobserved (unseen) data. Conducting a complete case analysis will produce unbiased estimates (but with a loss precision if full data are observed). Under the missing at random (MAR) assumption, the missingness after conditioning on the observed data does not depend on the unobserved (unseen) data. Under this approach, we can apply approaches such as multiple imputation, by fitting a joint model to the observed data and impute the missing data, taking account of the uncertainty in the estimated parameters of this joint model.

We feel this, MAR, approach makes a less strong and more realistic assumption than the MCAR approach. The MAR imputation model will include all variables considered for the multivariable model building, the outcome and any auxiliary variables that will help explain the missingness. The assumption of a missing not at random (MNAR) approach whilst not implausible is considerably more complex to investigate – there is a dearth of research investigating MNAR in the context of prediction model research. We will nevertheless explore whether the MAR assumption holds by comparing the imputed values (after accounting for the observed values) and the missing values to identify if there are any systematic differences to suggest a MNAR assumption.

Therefore, to conform to current guidelines[34], multiple imputation for all subjects with at least one missing value (using the 'mice' function in R, for example) will be used.

Data from LHCH and BHC provide a large "real-world" prospective validation but is likely to contain more missingness [35].

Using sensitivity analyses we may investigate the impact of informative missingness in our model development, i.e. departures from the missing at random assumption.

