11.7 The Level of Statistical Significance

The level of statistical significance will be set at p<0.05.

11.8 Procedure for Accounting for Missing, Unused, and Spurious Data.

To avoid excluding patients when developing and validating our models, we will use multiple imputation to impute missing values, under a missing at random assumption. Identifying the true underlying missing data mechanism from the available is rarely possible. Assumptions need to be made on the plausible mechanism, and approaches needed to be used. Under a missing completely at random mechanism.

Clinical Research Protocol Template version 15.0 CON © Copyright: The University of Oxford and Oxford University Hospitals NHS Foundation Trust 2019 Page 21 of 34

CONFIDENTIAL

(MCAR), the missingness mechanism does not depend on unobserved (unseen) data. Carrying out a complete case analysis will produce unbiased estimates (but with a loss precision if full data are observed). Under the missing at random (MAR) assumption, the missingness after conditioning on the observed data does not depend on the unobserved (unseen) data. Under this approach, we can apply approaches such as multiple imputation, by fitting a joint model to the observed data and impute the missing data, taking account of the uncertainty in the estimated parameters of this joint model. We feel this, MAR, approach makes a less strong and more realistic assumption than the MCAR approach. The MAR imputation model will include all variables considered for the multivariable model building, the outcome and any auxiliary variables that will help explain the missingness. The assumption of a missing not at random (MNAR) approach whilst not implausible is considerably more complex to investigate – there is a dearth of research investigating MNAR in the context of prediction model research. We will nevertheless explore whether the MAR assumption holds by comparing the imputed values (after accounting for the observed values) and the missing values to identify if there are any systematic differences to suggest a MNAR assumption.

Data from the NHS Trusts provide a large "real-world" prospective validation, but is likely to contain more missingness (60).

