### 2.1. AIM

This study aims to develop and validate two clinical prediction models to estimate the risk of a patient developing AF in the seven days following cardiac surgery, using data available:

- In the pre-operative assessment clinic or at admission for surgery (PARADISE-1)
- On arrival to the post-operative care unit (PARADISE-2)

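### Outcome-inclusive imputation in the validation data estimates performance with complete predictors; the plan has no analysis of performance when inputs are missing at the moment of prediction

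*SAP*

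**What the plan says.** SAP 3.4.1 opens with the scope of imputation: "To avoid excluding patients when developing and validating our models, we will use multiple imputation to impute missing values". The method assumes missing at random and covers "multiple imputation for all subjects with at least one missing value". Its content is then fixed: "The MAR imputation model will include all variables considered for the multivariable model building, the outcome and any auxiliary variables". Protocol 11.8 has the same rule. Neither document gives a separate rule for validation data.

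SAP 3.4.1 describes the data from two NHS centres as a large real-world "prospective validation but is likely to contain more missingness", and Protocol 11.8 says the same of the NHS Trusts. No missing rate is stated.

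SAP 2.1 fixes the time of use: the pre-operative clinic or admission for PARADISE-1, and arrival in post-operative care for PARADISE-2. SAP 3.8.2 says that the MGH model will be applied to each validation patient and the predictions compared with observed outcomes. It does not say what happens when a user lacks an input. The only missing-data sensitivity analysis, in SAP 3.4.1, is optional, concerns departures from missing at random, and is confined to model development.

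**The concern.** Including the outcome is right when coefficients are estimated. In a validation set the same choice fixes which quantity is reported. A missing predictor is drawn partly from knowledge of whether that patient went on to have atrial fibrillation, which restores the association the predictor would have shown had it been recorded. The result is performance with complete predictors.

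A user with a missing input has no outcome to draw on and must impute from what is known at that time, or not use the score. The two quantities differ even when data are missing completely at random, so the planned check on departures from missing at random would not show the difference.

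External discrimination and calibration are the primary outcome (Protocol section 6), and the NHS cohort is the routine-care test of the scores. A reader could take its C-statistic to cover patients with incomplete records, which the planned analysis does not address.

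**Working it through.** **Inputs from the documents (SAP 3.8.2).** Prevalence 20%; anticipated C about 0.72; intercept 0 and slope 1; about 6,000 NHS patients a year, with 2,000 events.

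**The plan's own figures.**
- O/E: n = (1 − φ)/(φ × SE²) = 0.8/(0.2 × 0.051²) = 1,538, as stated.
- C-statistic, Newcombe-type standard error, interval width 0.1: 619 at C = 0.72, 531 at 0.77 and 692 at 0.67 (stated 619, 531, 691).
- Calibration slope, normal linear predictor with common variance: 4,243 to 4,252 at C = 0.725 (stated 4,248). At exactly 0.720 it is about 4% higher, which is consistent with rounding of the stated value.

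These sample sizes do not depend on the point made here and are unchanged by it.

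**Assumptions the documents do not supply.** Missing rate, the share of the signal in the missing predictors, and the correlation between predictors. Ranges are shown for the first two.

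**Check 1: two blocks of predictors.** N = 6,000, 60 replicates, 10 imputations, full-data C about 0.72, correlation 0.2 between blocks. One block is always observed; the other, carrying half the signal, is missing completely at random.

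| Missing | With outcome (planned) | Without outcome, conditional mean: C (slope) | Without outcome, random draws: C (slope) |
|---|---|---|---|
| 10% | 0.719 | 0.714 (0.99) | 0.710 (0.95) |
| 30% | 0.721 | 0.707 (1.00) | 0.695 (0.86) |
| 50% | 0.720 | 0.696 (0.98) | 0.676 (0.77) |

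At 30% missing, conditional-mean imputation gives 0.713 if the block carries 30% of the signal and 0.696 if it carries 80%.

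Hand check for patients whose block is missing. With a normal linear predictor, C = Φ(s/√2), so s/√2 = Φ⁻¹(0.72) = 0.583. Take equal weights of √0.5 and correlation 0.2:
- total variance = 0.5 + 0.5 + 2 × 0.2 × 0.5 = 1.2;
- part predictable from the observed block = (0.707 + 0.2 × 0.707)² = 0.72;
- ratio = 0.72/1.2 = 0.6;
- attainable C ≈ Φ(0.583 × √0.6) = Φ(0.451) = 0.67.

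The simulation gives 0.668 to 0.672 for these patients, against about 0.72 from the planned imputation.

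**Check 2: six predictors correlated 0.15, with the two strongest missing completely at random.** Full-data C is 0.720. With the outcome, C is 0.719 to 0.720 throughout. Without it, by conditional mean:
- 10% missing: 0.715, a loss of 0.005
- 20% missing: 0.709, a loss of 0.011
- 30% missing: 0.703, a loss of 0.017
- 40% missing: 0.697, a loss of 0.023

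Slopes are 0.97 to 0.99.

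**Check 3: a dominant predictor always recorded.** Protocol 5.1 reports 0.66 for age alone against 0.68 for the best published model. Set age-only C to about 0.66, full C to about 0.72, and let two of five equal weaker predictors be missing. The losses are then about 0.003, 0.004 and 0.006 at 20%, 30% and 40% missing. With three of the five missing they are 0.004, 0.007 and 0.009.

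**Scale.** At N = 6,000 and C = 0.72 the 95% half-width is 1.96 × 0.0082 = 0.016 at 20% prevalence, and 1.96 × 0.0069 = 0.014 at one third.

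**The case against.** The strongest reply is that nothing is biased against the stated target. The primary outcome is the models' discrimination and calibration in external data, and the planned method recovers the complete-data C at every missing rate tried. This stands. A reader might infer that the plan inflates its NHS results. The documents do not support that: if users always have every input, there is no overstatement.

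Second, a gap in a research extract is not a gap in clinic. Protocol 12.2 says that some variables, such as echocardiographic findings, may be absent from structured sources and will be extracted by nurses from the electronic record. A clinician may see a value that the extract lacks, so an outcome-free analysis could understate performance in use. This stands too, and it is why that analysis should not replace the planned one.

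Third, the size depends on the scenario. Losses of about 0.04, and slopes well below 1, arise when each missing value is a random draw, an unlikely way to run a clinical score. They also arise by conditional mean when the missing block carries 80% of the signal and half its values are missing. Under Check 3 the losses fall within the confidence interval for C.

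Fourth, a reader might infer that later values will leak into PARADISE-1's missing pre-operative inputs. The imputation rule permits this on a literal reading, but SAP 3.3 says that the two models use different predictors, and the SAP does not say that one imputation serves both. Under missing at random, later variables used as auxiliaries would still target complete-predictor performance.

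What remains is that neither document says which performance the validation estimates, and no planned analysis covers missing inputs.

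**Conclusion.** The point holds as a gap in what is estimated and reported; the imputation method itself is not in error. The planned validation answers how the scores perform with complete predictors. It leaves open how they perform when inputs are missing, in the cohort expected to have most missing data.

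With 10% to 40% missing in strong predictors, imputed by conditional mean, the difference in C is about 0.005 to 0.02 with slope near 1, so the effect is on discrimination and hardly on the calibration slope. At the lower end it lies inside the confidence interval at N = 6,000. It shrinks further if the strongest predictor is always recorded, and grows if the missing predictors carry most of the signal. All of these sizes rest on assumed missing rates and predictor weights. Only the direction and the absence of an outcome-free analysis are firm.

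**What to change.** Keep the outcome-inclusive imputation for development and as the planned validation estimate, and label the latter in the SAP and reports as performance with complete predictors.

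For the NHS cohort, pre-specify one co-reported analysis for each score:
- fit the imputation model in the MGH data and freeze it;
- exclude the outcome;
- use only variables available when that score is applied, so no intra- or post-operative values for PARADISE-1;
- state the form of imputation (conditional mean or random draws), because it affects the slope;
- report C, calibration intercept and slope beside the planned result, with the proportion missing for each predictor.

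Describe it as performance if missingness in use matches that in the extract, and do not make it the only basis for NHS conclusions. The documents flag heavier missingness only for the NHS data, so Brigham and Tight K need not be included.

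The cost is one extra analysis for each score on data already collected, and possibly a slightly lower C reported alongside the planned one. If missingness proves low, the two results will agree and the report can show it.
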